## 7.0 REGULATORY AND REPORTING REQUIREMENTS

### 7.1 Adverse Event Reporting for MD Anderson-Sponsored IND Protocols

All adverse events that are possible, probably or definitely related to the study treatment will be captured on the case report form. Any grade 3 or higher adverse event that is considered unrelated or unlikely related to the study treatment will also be recorded. Adverse events will be defined using NCI CTCAE version 4.03.

All adverse events occurring between the time the subject is consented and begins study drug will be considered a baseline event and recorded. Baseline adverse events will be recorded in the Clinical Oncology Research System (CORE). All baseline adverse events that increase in severity during the course of treatment will be captured as an adverse event in CORE.

### 7.2 Serious Adverse Event Reporting (SAE) for M. D. Anderson-Sponsored IND Protocols

An adverse event or suspected adverse reaction is considered “serious” if, in the view of either the investigator or the sponsor, it results in any of the following outcomes:

- Death
- A life-threatening adverse drug experience – any adverse experience that places the patient, in the view of the initial reporter, at immediate risk of death from the adverse experience as it occurred. It does not include an adverse experience that, had it occurred in a more severe form, might have caused death.
- Inpatient hospitalization or prolongation of existing hospitalization
- A persistent or significant incapacity or substantial disruption of the ability to conduct normal life functions.
- A congenital anomaly/birth defect.

Any serious adverse event that occurs during the study period (up through 100 days after the last day drug is administered) will be followed until clinical recovery is complete and laboratory tests have returned to normal, until progression of the event has been stabilized, or until the PI determines there has been acceptable resolution of the event. The PI or designee will be responsible for assigning attribution for all SAEs.

Important medical events that may not result in death, be life-threatening, or require hospitalization may be considered a serious adverse drug experience when, based upon appropriate medical judgment, they may jeopardize the patient or subject and may require medical or surgical intervention to prevent one of the outcomes listed in this definition. Examples of such medical events include allergic bronchospasm requiring intensive treatment in an emergency room or at home, blood dyscrasias or convulsions that do not result in inpatient hospitalization, or the development of drug dependency or drug abuse (21 CFR 312.32). Pregnancy, overdose and secondary malignancy will be handled as SAE.

- Important medical events as defined above may also be considered serious adverse events. Any important medical event can and should be reported as an SAE if deemed appropriate by the Principal Investigator or the IND Sponsor, IND Office.
- All events occurring during the conduct of a protocol and meeting the definition of a SAE must be reported to the IRB in accordance with the timeframes and procedures as per “The University of Texas M. D. Anderson Cancer Center Institutional Review Board Policy for Investigators on Reporting Unanticipated Adverse Events for Drugs and Devices”. Unless stated otherwise in the protocol, all SAEs, expected or unexpected, must be reported to the IRB, regardless of attribution (within 5 working days of knowledge of the event).
- All life-threatening or fatal events, that are unexpected, and related to the study drug, must have a written report submitted within 24 hours (next working day) of knowledge of the event to the Safety Project Manager in the IND Office.
- Unless otherwise noted, the electronic SAE application (eSAE) will be utilized for safety reporting to and MDACC IRB.
- Serious adverse events will be captured from the time of the first protocol-specific intervention, until 100 days after the last dose of drug, unless the participant withdraws consent. Serious adverse events must be followed until clinical recovery is complete and laboratory tests have returned to baseline, progression of the event has stabilized, or there has been acceptable resolution of the event.
- Additionally, any serious adverse events that occur after the 100 day time period that are related to the study treatment must be reported to the IND Office. This may include the development of a secondary malignancy.

**Reporting to FDA:** Serious adverse events will be forwarded to FDA by the IND Sponsor (Safety Project Manager IND Office) according to 21 CFR 312.32. It is the responsibility of the PI and the research team to ensure serious adverse events are reported according to the Code of Federal Regulations, Good Clinical Practices, the protocol guidelines, the sponsor’s guidelines, and Institutional Review Board policy.

**Reporting by investigator to BMS:** The investigator will inform BMS of any SAE within 24 hours of being aware of the event via email and/or fax. **All SAEs should be reported via confirmed facsimile (fax) transmission, or scanned and reported via electronic mail to:**

**SAE Email Address:** [contact]

**SAE [contact]

The following SAEs are not subject to expedited reporting, but will be included in the annual report via the SAE log: Infection or cytopenias leading to hospitalization or prolongation of hospitalization; disease progression leading to death; life-threatening AE, hospitalization or prolongation of hospitalization, or disability.

Adverse events will be documented in the medical record and entered into the case report form. PDMS/CORE will be used as the electronic case report form for this protocol. Investigator or physician designee is responsible for verifying and providing source documentation for all adverse events and assigning the attribution for each event for all subjects enrolled on the trial. This form must be completed and supplied to BMS within 24 hours/1 business day at the latest on

the following working day. The initial report must be as complete as possible, including details of the current illness and (serious) adverse event, and an assessment of the causal relationship between the event and the investigational product(s). Information not available at the time of the initial report (e.g., an end date for the adverse event or laboratory values received after the report) must be documented on a follow-up MDACC SAE reporting form.

Pregnancies and suspected pregnancies (including a positive pregnancy test regardless of age or disease state) of a female subject or the female partner of a male subject occurring while the subject is on study drug, or within 30 days of the subject's last dose of study drug, are considered immediately reportable events. Study drug is to be discontinued immediately in a female patient and the patient instructed to return any unused portion of the study drug to the investigator(s). The pregnancy, suspected pregnancy, or positive pregnancy test must be reported to BMS immediately by phone and facsimile using the MDACC AE report form. The female should be referred to an obstetrician-gynecologist experienced in reproductive toxicity for further evaluation and counseling.

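### As punctuated, the Section 7.2 exemption from expedited reporting covers any life-threatening event, hospitalization or disability and contradicts that section's two 24-hour rules

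*Combined protocol and SAP*

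**What the plan says.** All the rules at issue are in Section 7.2 of the combined protocol and SAP.

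- **Exemption.** It opens: "The following SAEs are not subject to expedited reporting, but will be included in the annual report via the SAE log". The list has three groups separated by semicolons. The first two are "Infection or cytopenias leading to hospitalization or prolongation of hospitalization; disease progression leading to death". The third is "life-threatening AE, hospitalization or prolongation of hospitalization, or disability". No recipient (IRB, IND Office, FDA or BMS) is named, and no group is limited by attribution or expectedness.
- **IND Office.** Life-threatening or fatal events that are both unexpected and drug related "must have a written report submitted within 24 hours (next working day) of knowledge of the event". No exception is stated.
- **BMS.** "The investigator will inform BMS of any SAE within 24 hours of being aware of the event via email and/or fax". No exception is stated. The paragraph after the exemption sets the limit again: "This form must be completed and supplied to BMS within 24 hours/1 business day at the latest on" the next working day.
- **IRB.** Every SAE is reported within 5 working days, expected or not and whatever its attribution. This rule opens with a proviso that lets the protocol provide differently.
- **FDA.** The IND sponsor forwards SAEs under 21 CFR 312.32. The documents give no timeline.

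The seriousness definition in the same section bullets five outcomes: death, life-threatening experience, hospitalization or its prolongation, incapacity, and congenital anomaly. Important medical events are added separately.

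**The concern.** A coordinator applying the exemption as printed could put a drug-related, unexpected, life-threatening event in a log for the annual report. A few lines earlier, the same section requires a written report on that event by the next working day. The text does not say which instruction prevails, or whether the exemption is addressed to the IRB, the IND Office, the FDA, BMS or all of them. At stake is timely notice to parties outside the study team, for a drug whose serious events may be immune-mediated and need early recognition, as Sections 5.2 and 5.4 say.

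**Working it through.** No arithmetic beyond a count applies. The check sets the exemption against each reporting rule under two readings.

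**Literal reading.** The third group stands alone, so any life-threatening event, hospitalization or disability is exempt.

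**Narrower reading.** The semicolon after the death item is taken as a slip, so that death, life-threatening event, hospitalization and disability all depend on disease progression. The infection and cytopenia group is unchanged.

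| Rule in Section 7.2 | Literal reading | Narrower reading |
|---|---|---|
| IND Office, 24 hours, unexpected and related life-threatening or fatal events | Contradicted: a life-threatening event is exempt whatever its cause | Mostly resolved. A related, unexpected, life-threatening infection or cytopenia that leads to hospitalization still falls under both provisions |
| BMS, 24 hours, any SAE | Contradicted | Still contradicted: hospitalized infection or cytopenia and serious progression events meet the SAE definition |
| IRB, 5 working days, all SAEs | Suspended through the proviso, not contradicted; the rule loses most of its content | Suspended for a much smaller set of events |
| FDA, under 21 CFR 312.32 | No timeline in the documents to compare | Same |

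**Extent of the literal exemption.** Of the five bulleted outcomes, the third group covers life-threatening experience, hospitalization and disability (incapacity), so 3 of 5. The second group adds deaths from progression. What remains under the ordinary rules is deaths from other causes (unless already exempt through the hospitalization they followed), congenital anomalies, and important medical events that meet none of the exempted outcomes.

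**Which reading was meant.** If every hospitalization were exempt, the first group, which exempts hospitalization for infection or cytopenia, would add nothing. That redundancy suggests that the last phrases were meant to follow disease progression. It is evidence of intent and does not change the instruction as printed.

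**Does the exemption reach the toxicity stopping rule?** Section 9.0 counts Grade 3-4 clinically relevant non-hematologic toxicity, or an SAE at least possibly drug related, and applies the rule in cohorts of 5. These data have their own route. Adverse events are assessed continuously (Section 5.6, Evaluation During Study). Related events go on the case report form (Section 7.1). The PI or a designee attributes every SAE (Section 7.2). Events are entered in CORE (Sections 7.2 and 8.0). The exemption alters none of these steps, and nothing ties the stopping count to expedited reports.

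**The case against.** The strongest reply is that this is one misplaced semicolon. The literal reading makes the first group redundant, the sensible reading is clear, and on it most of the IND Office conflict goes. The text was also read from PDF by a program, so the mark cannot be checked against the source here. This stands as an argument about intent and limits the severity. It does not remove the BMS conflict, which is present on both readings.

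A second reply is that the exemption may have been meant for some recipients only, and not for BMS. If so, the BMS conflict would fall away, but the sentence does not say so, and that silence is itself part of the defect.

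Three stronger inferences are tempting, and the documents do not support them:

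- A reader might infer that the exemption contradicts the 5-working-day IRB rule. It does not, because the rule allows the protocol to provide otherwise and the exemption does so. The fair criticism is that the literal exception is so wide, drug-related events included, that little of the rule is left.
- A reader might infer that the toxicity stop would be delayed, since drug-related SAEs count toward it. The count rests on events captured and attributed in CORE at a single center, so a delay is not shown.
- A reader might infer a delay of up to 12 months from the annual report. That is a worst case which assumes that the exemption overrides every other deadline in Section 7.2, and no text says that.

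Finally, whether related infections and cytopenias should be exempt is partly a policy choice. The institutional IRB policy that Section 7.2 cites is not available here. The point is therefore put as a need to reconcile the provisions.

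**Conclusion.** The exemption is wrong as written. Its third item lifts expedited reporting for three of the five bulleted seriousness outcomes without limit on cause, expectedness or attribution. That contradicts the 24-hour rules to the IND Office and to BMS, and it suspends the IRB rule for the same categories. If the semicolon is a slip, the IND Office conflict shrinks to related, unexpected, life-threatening infections or cytopenias with hospitalization, while the BMS conflict remains for every exempted event.

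The consequence is possible late notice of SAEs outside the study team. Its length cannot be stated from the documents. Endpoints, sample size and analysis are untouched. The conclusion assumes that the extracted punctuation matches the source and that the exemption, naming no recipient, may be taken to apply to all of them. The correction should be made because this is an operative safety-reporting instruction that contradicts itself.

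**What to change.** Rewrite the exemption in Section 7.2 so that it:

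1. exempts life-threatening events, hospitalization and disability only when they are due to disease progression;
2. names the recipient and the timeline to which the exemption applies;
3. states that it does not override the 24-hour rules to the IND Office and to BMS;
4. reconciles the infection and cytopenia item with those rules, saying how related or unexpected events are handled.

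If the sponsor does intend some events to be exempt from the BMS deadline, the BMS rule and its repetition after the exemption should say so. The cost is one sentence and possibly a few more expedited reports. No change to the design or the analysis is needed.

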## **8.0 DATA HANDLING**

PDMS will be used as the database for this study. All adverse events will be reported in CORE.

## **9.0 STATISTICAL CONSIDERATIONS**

This is a single-center phase II trial to determine the efficacy of nivolumab as a monotherapy in subjects with Primary, Post Polycythemia Vera, or Post Essential Thrombocythemia Myelofibrosis (PMF, post-PV MF, or post-ET MF). The primary endpoint is the objective response rate (ORR) after 8 doses of therapy (4 cycles), defined as CR (complete remission) + PR (partial remission) + CI (clinical improvement). Responses will be categorized according to the revised International Working Group-Myeloproliferative Neoplasms Research and Treatment (IWG-MRT) and European LeukemiaNet (ELN) consensus criteria for myelofibrosis.

An optimum two-stage design proposed by Simon will be implemented. We assume a target ORR of 35%, and a response rate of 18% or lower will be considered not desirable. With a type I error rate of 7% and 80% power, we will enroll 16 patients in the first stage. If 3 or fewer patients achieve a response the trial will be stopped. If 4 or more out of the first 16 patients have a response, accrual will continue until a total of 40 patients have been enrolled. After the first 16 patients have enrolled, the study will not enroll new patient until enough responses (at least 4 responses out of 16 patients) are observed to warrant the continuation of the study. At the end of the study, if 11 or more out of these 40 patients achieve a response, the treatment of nivolumab will be considered efficacious and worth further investigation. Under this Simon's Optimum two-stage design, the probability of early termination is 68% if the true ORR is 18% and the expected sample size is 23.7 patients. Patients will be enrolled from MDACC and patients will be registered through the Clinical Oncology Research System (CORE). The estimated accrual rate is 1-2 patients per month. An interim analysis (response summary) will be submitted to the IND Monitor following the treatment of 16 and 40 patients.

The method of Thall, Simon and Estey will be used for toxicity monitoring for this study. Toxicity will be monitored among the 40 patients. Denote the probability of toxicity by  $p(T)$ ,

where toxicity is defined as Grade 3-4 clinically relevant non-hematologic toxicity or a serious adverse event that is at least possibly drug related (Common Terminology Criteria for Adverse Events CTCAE version 4.03) and occurs anytime during the treatment. We assume as a priori,  $p(T) \sim \text{beta}(0.6, 1.4)$ . We will stop treating patients if  $\text{Pr}(p(T) > 0.30 \mid \text{data}) > 0.9$ . That is, we will stop the trial for new patient enrollment if at any time during the study, we determine that there is more than 90% chance that the toxicity rate is more than 30%. This toxicity stopping rule will be applied by cohort size of 5, starting from the 5th patient. Stopping boundaries corresponding to this stopping rule are listed in table 8.a. The operating characteristics are summarized in Table 8.b. Multc Lean Desktop (version 2.0) was used to generate the toxicity stopping boundaries and the OC table.

**Table 8.a Boundary table for toxicity monitoring**

# of patients ( in cohort of 5, starting from the 5 th patient)	Stop the trial if there are this many patients with toxicities:
5	4-5
10	6-10
15	8-15
20	9-20
25	11-25
30	13-30
35	15-35

**Table 8.b. Operating characteristics for toxicity monitoring**

True toxicity rate	Prob(stop the trial early)	Average sample size
0.1	0.0006	40
0.2	0.021	39
0.3	0.186	36
0.4	0.583	27
0.5	0.905	17

Summary statistics will be provided for continuous variables. Frequency tables will be used to summarize categorical variables. The objective response rate (ORR) will be estimated along with the exact 95% confidence interval. Data from all subjects who receive any study drug will be included in the safety analyses. The severity of the toxicities will be graded according to the NCI CTCAE v4.03 whenever possible. We will follow standard reporting guidelines for adverse

events. Safety data will be summarized by category, severity and frequency. The proportion of patients with AEs will be estimated, along with the Bayesian 95% credible intervals.

**Duration of response:** Duration of response is defined as the date at which the subject's objective status is first noted to be a CR, PR or CI to the date of progression (no longer meeting criteria for either CR, PR or CI) is documented (if one has occurred). Patients who continue to respond as of the data cut-off date will be censored as of the date of their last assessment documenting continued response.

**Time to response:** The time to response is defined as the time from study registration to the first date at which the subject's objective status was classified as a response (CR, PR or CI). In subjects who do not achieve a response, time to response will be censored at the subject's last evaluation date.

The distribution for each of these event-time variables (duration of response and time to response) will be estimated by Kaplan-Meier curves.

**Anemia:** Descriptive statistics will be used to explore improvements in anemia and transfusion dependence. The following outcomes will be summarized: mean changes in hemoglobin at monthly intervals. The proportion of transfusion independent patients not requiring transfusions on study who experience an increase of 2 g/dL in their hemoglobin relative to baseline, the proportion of transfusion dependent patients (defined as requiring a transfusion of 2 units PRBCs monthly for 3 months (12 weeks) prior to starting the trial) who become transfusion independent (not requiring a transfusion of PRBCs over a period of 3 months (12 weeks) while on study), the proportion of transfusion dependent patients who become transfusion independent and have a 1 g/dL increase in hemoglobin relative to baseline, and the proportion of transfusion independent patients requiring a transfusion while on study.

**JAK2V617F Allele burden:** Change in JAK2V617 allele burden from baseline to each visit where it is measured.

**Correlative Studies:** Descriptive statistics including plots, mean, median and standard deviations will be used to summarize data. For continuous outcomes, t-test and ANOVA will be used to compare outcome measures across patient characteristics. Dunnett's and Tukey's test that properly adjust for multiplicity in multiple tests will be implemented. Pair-wise comparisons will be performed using pre- and post-therapy samples from each patient. The chi-square (c2) test or Fisher's exact test will be used to test the association between two categorical variables such as disease state and performance status.

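### Does an exact 95% interval that contains 18% at 11 or 12 responders of 40 contradict the success rule or its stated 7% error?

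*Combined protocol and SAP*

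**What the plan says.** The design is in Section 9.0, Statistical Considerations. The hypotheses are: "We assume a target ORR of 35%, and a response rate of 18% or lower will be considered not desirable". The error rates and first-stage size are: "With a type I error rate of 7% and 80% power, we will enroll 16 patients in the first stage". The interim rule is: "If 3 or fewer patients achieve a response the trial will be stopped". Otherwise "accrual will continue until a total of 40 patients have been enrolled", and at the end "if 11 or more out of these 40 patients achieve a response, the treatment of nivolumab will be considered efficacious and worth further investigation". The same paragraph gives a 68% probability of early termination and an expected sample size of 23.7, both at a true rate of 18%.

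The analysis text after Table 8.b, still in Section 9.0, has one sentence on the primary endpoint: "The objective response rate (ORR) will be estimated along with the exact 95% confidence interval". It does not name the interval method, say whether the interval allows for the interim stop, or give the interval a part in the decision. The section does not say that the test is one-sided, although a Simon design is.

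**The concern.** Three things seem not to fit together.

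- **Type I error.** The exact value for the stated cut-offs is a little above 7%. If 7% were a strict ceiling, 16/40 would not be the optimum design.
- **Decision against interval.** A trial ending at 11 or 12 responders would be called efficacious beside an interval that reaches below 18%. A reader could ask which of the two governs.
- **Estimation after an interim stop.** The observed proportion and an ordinary exact interval treat the patients as one fixed sample. Because the trial can stop early only on poor results, the proportion is biased downward on average, and that estimate may feed the planning of a later trial.

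This is the primary endpoint, and the outcome is not rare. At a true rate of 35% the chance of finishing at 11 or 12 responders is 15.1%.

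**Working it through.** **Inputs** (all from Section 9.0): p0 = 0.18, p1 = 0.35; first stage n1 = 16, stop at X1 ≤ 3; total n = 40, so n2 = 24; success at 11 or more.

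**1. Reproduce the plan's figures.**

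- Early termination: PET(p) = P(X1 ≤ 3 | 16, p). At 18% this is 0.6777 (stated 68%).
- Expected size: 16 + (1 − 0.6777) × 24 = 23.74 (stated 23.7).
- P(success | p) = Σ over x = 4 to 16 of b(x; 16, p) × P(X2 ≥ 11 − x | 24, p). At 35% this is 0.8018 (stated 80%). At 18% it is 0.07295 (stated 7%).

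All four agree with the plan at the precision it uses. A search for the design with the smallest expected size returns exactly 3/16, 10/40 when the error ceiling is 7.5% or 8%. Under a ceiling of exactly 7.0% it returns 3/16, 11/44 (error 6.6%, power 80.9%, expected size 25.0).

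**2. Interval against decision.** The p-value is P(at least this many responders, with the interim rule applied, | 18%). The two-stage interval uses stage-wise ordering.

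| Result | One-sided p | Ordinary exact 95% interval | Two-stage 95% interval |
|---|---|---|---|
| 11/40 | 0.073 | 14.6% to 43.9% | 15.1% to 47.1% |
| 12/40 | 0.038 | 16.6% to 46.5% | 16.9% to 48.5% |
| 13/40 | 0.018 | 18.6% to 49.1% | 18.8% to 50.2% |

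A two-sided 95% interval excludes 18% from below only when the one-sided p-value is about 0.025 or less. The success rule accepts p up to 0.073. Results with p between those values, here 11 and 12, succeed with 18% inside the interval by either method. If the interval had to exclude 18%, the bar would be 13/40, with type I error 1.8% and power 65.1%.

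An interval at the decision's own level has confidence 1 − 2 × 0.073 = 85.4%. The two-stage version at 11/40 is 18.0% to 42.2%. Its lower limit is 18.0% by construction, because the level was chosen from the p-value at 11/40.

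**3. Coverage of the 95% intervals.**

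| True rate | Ordinary exact | Two-stage |
|---|---|---|
| 18% | 0.982 | 0.982 |
| 30% | 0.979 | 0.982 |
| 35% | 0.970 | 0.973 |

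The ordinary interval is conservative at these rates. The two-stage interval covers almost equally often and is wider at 11/40: 47.1 − 15.1 = 32.0 points against 43.9 − 14.6 = 29.3.

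**4. Point estimate.** The bias of the observed proportion over all trials is −2.2 points at 18%, −2.1 at 30% and −1.5 at 35%. The uniformly minimum variance unbiased estimate (UMVUE) removes it; at 11/40 it is 31.4% against 27.5%. Among successful trials only, the means are:

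| True rate | Observed proportion | UMVUE |
|---|---|---|
| 18% | 29.8% | 32.9% |
| 30% | 34.1% | 36.1% |
| 35% | 37.2% | 38.6% |

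Both are too high after a success, the UMVUE more so. Its root mean squared error is larger at low rates (0.092 against 0.075 at 18%; 0.096 against 0.090 at 25%) and slightly smaller at 30% to 35%.

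**The case for a change.** The best case for a change is that different levels do not explain everything. The ordinary exact interval at the decision's own 85.4% level is 17.3% to 39.9% at 11/40 and still contains 18%. Only an interval that respects the two stages agrees with the rule. Borderline results make up 15.1 / 80.2 = 19% of successes at a true 35%, and 5.5 / 7.3, about three quarters, of false successes at 18%. The plan names no estimator, so one chosen after the data are known could look driven by the result, and a few added sentences would cost little.

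These facts stand. They show that an ordinary exact interval is not the inverse of a two-stage test, but the plan never uses it as one. The matching 85.4% interval restates the 11/40 rule and tells the reader nothing further. The worry about later choice is limited: the cut-off is fixed in advance, and the observed proportion with an exact interval is the natural reading of the plan's sentence. Saying that the test is one-sided, that its exact error is 7.3%, and that the count governs would be harmless, as would showing two-stage estimates as a supplement. An analyst can do this in the report without altering the plan.

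**Conclusion.** The arithmetic behind the concern is right, but it requires no change. The type I error exceeds the stated figure by 7.3 − 7.0 = 0.3 points, which is rounding of the same kind as 67.8% given as 68%. That reading assumes 7% is a rounded error rate and not a hard ceiling; the plan does not call it a ceiling.

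The rule and the interval do different work. Success depends only on 11 or more of 40 and means that further study is worthwhile; the interval describes precision. Their disagreement at 11 and 12 responders follows from testing at about 7% one-sided and estimating at 2.5% per tail.

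The alternatives bring no clear gain. The two-stage 95% interval has nearly the same coverage, is wider at 11/40 and still contains 18% at both counts. The UMVUE removes an average bias of about 1.5 to 2.5 points but adds 1.4 to 3.1 points to the mean estimate among successful trials (38.6 − 37.2 at a true 35%; 32.9 − 29.8 at 18%), the trials most likely to inform a next study. The comparison assumes that the unnamed exact interval is the ordinary fixed-sample one. If it was meant to be the two-stage interval, the concern about ignoring the interim stop falls away for the interval. The sample size, the cut-offs and the decision are unaffected either way.
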